**Table 1. Adequate Organ Function Laboratory Values**

System	Laboratory Value
Hematological	
Absolute neutrophil count (ANC)	$\geq 1500/\mu\text{L}$
Platelets	$\geq 100\,000/\mu\text{L}$
Hemoglobin	$\geq 9.0\text{ g/dL}$ or $\geq 5.6\text{ mmol/L}^{\text{a}}$
Renal	
Serum Creatinine Measured or calculated b creatinine clearance (GFR can be used in place of creatinine or clearance; 24-hour urine collection can be used for more accurate estimate as needed)	$\leq 1.5 \times \text{ULN}$ OR calculated creatinine clearance (GFR can be used in place of creatinine or creatinine clearance) $\geq 50\text{ml/min}$
Hepatic	
Total bilirubin	$\leq 1.5 \times \text{ULN}$ OR direct bilirubin $\leq \text{ULN}$ for participants with total bilirubin levels $>1.5 \times \text{ULN}$
AST (SGOT) and ALT (SGPT)	$\leq 2.5 \times \text{ULN}$
Coagulation	
International normalized ratio (INR) OR prothrombin time (PT) Activated partial thromboplastin time (aPTT)	$\leq 1.5 \times \text{ULN}$ unless participant is receiving anticoagulant therapy, as long as PT or aPTT is within therapeutic range of intended use of anticoagulants
ALT (SGPT)=alanine aminotransferase (serum glutamic pyruvic transaminase); AST (SGOT)=aspartate aminotransferase (serum glutamic oxaloacetic transaminase); GFR=glomerular filtration rate; ULN=upper limit of normal.	
a Criteria must be met without erythropoietin dependency and without packed red blood cell (pRBC) transfusion within last 2 weeks.	
b Creatinine clearance (CrCl) should be calculated per institutional standard.	

Note: This table includes eligibility-defining laboratory value requirements for treatment; laboratory value requirements should be adapted according to local regulations and guidelines for the administration of specific chemotherapies.

### 5.1.2 Participant Exclusion Criteria

Participants are excluded from the study if any of the following criteria apply:

1. A WOCBP who has a positive urine pregnancy test within 72 hours prior to enrolment (see Appendix 2). If the urine test is positive or cannot be confirmed as negative, a serum pregnancy test will be required.
2. Patients with pure small cell histology will be excluded. Mixed histology including partial neuroendocrine small cell features will be permitted.
3. Patients considered to be medically unfit for accelerated (dose dense) MVAC chemotherapy, TURBT or RC (per Investigator discretion) will be excluded.
4. Has received prior therapy with an anti-PD-1, anti-PD-L1, or anti-PD-L2 agent or with an agent directed to another stimulatory or co-inhibitory T-cell receptor (e.g., CTLA-4, OX-40, CD137).
5. Has received prior systemic anti-cancer therapy including investigational agents within 4 weeks. Intravesical therapies are allowed without specified treatment interval.

Note: Participants must have recovered from all AEs due to previous systemic therapies to  $\leq$ Grade 1 or baseline. If participant had major surgery, they must have recovered adequately from the toxicity and/or complications from the intervention prior to starting study treatment.

6. Has received prior radiotherapy within 2 weeks of start of study treatment. Participants must have recovered from all radiation-related toxicities, not require corticosteroids, and should not have active radiation pneumonitis.
7. Has received a live vaccine within 30 days prior to the first dose of study drug. Examples of live vaccines include, but are not limited to, the following: measles, mumps, rubella, a version of varicella/zoster (chicken pox), yellow fever, rabies, *Bacillus Calmette–Guérin* (BCG), and typhoid vaccine. Seasonal influenza vaccines for injection are generally killed virus vaccines and are allowed; however, intranasal influenza vaccines (eg, FluMist®) are live attenuated vaccines and are not allowed.
8. Is currently participating in or has participated in a study of an investigational agent or has used an investigational device within 4 weeks prior to the first dose of study treatment.

Note: Participants who have entered the follow-up phase of an investigational study may participate as long as it has been 4 weeks after the last dose of the previous investigational agent.

9. Has diagnosis of immunodeficiency or is receiving chronic systemic steroid therapy (in dosing > 10 mg daily of prednisone dose equivalent) or any other form of immunosuppressive therapy within 7 days prior to the first dose of study drug.
10. Has known additional malignancy that is progressing or has required active systemic treatment within the past 2 years. Note: Participants with basal cell carcinoma or squamous cell carcinoma of the skin, or any carcinoma *in situ* that have undergone potentially curative therapy are not excluded. Low/intermediate risk prostate cancer with prior potentially curative therapy, or no intent of future systemic therapy and/or radiation is allowed. Non-invasive (Tis, Ta) upper urinary tract (renal pelvis/ureter) is allowed. Urethra cancer with prior curative intent therapy with no active recurrence is also allowed regardless of time elapsed.
11. Has known locally advanced (unresectable) or metastatic cancer on baseline radiographic imaging (CT or MRI) obtained within 28 days prior to study registration.
12. Has severe hypersensitivity ( $\geq$ Grade 3) to pembrolizumab and/or any of its excipients.
13. Has active autoimmune disease that has required systemic treatment in the past 2 years (i.e. with use of disease modifying agents, corticosteroids or immunosuppressive drugs). Replacement therapy (e.g., thyroxine, insulin, or physiologic corticosteroid replacement therapy for adrenal or pituitary insufficiency, etc.) is not considered a form of systemic treatment and is allowed. Note: Patients with active well controlled type 1 diabetes mellitus, vitiligo, Graves' disease, Hashimoto disease, eczema, lichen simplex chronicus, or psoriasis, not requiring systemic immunosuppression within the past 2 years are not excluded.
14. Has history of (non-infectious) pneumonitis that required steroids or has current pneumonitis.
15. Has an active infection requiring systemic therapy.
16. Has known history of Human Immunodeficiency Virus (HIV). Note: no HIV testing is required.
17. Has known history of active Hepatitis B (defined as Hepatitis B surface antigen [HBsAg] detected) or known active Hepatitis C virus (defined as HCV RNA [qualitative] detected) infection. Note: no testing for Hepatitis B and Hepatitis C is required.
18. Has known history of active TB (Bacillus Tuberculosis). Note: no testing is required unless it is clinically indicated

19. Has history or current evidence of any condition, therapy, or laboratory abnormality that might confound the results of the study, interfere with the subject's participation for the full duration of the study, or is not in the best interest of the subject to participate, in the opinion of the treating investigator.
20. Has known psychiatric or substance abuse disorders that would interfere with cooperation with the requirements of the trial.
21. Has had allogeneic solid visceral organ transplant.

### **5.1.3 Lifestyle Restrictions**

#### **5.1.3.1 Meals and Dietary Restrictions**

Participants should maintain a normal diet unless modifications are required to manage an AE such as diarrhea, nausea or vomiting.

#### **5.1.3.2 Contraception**

Pembrolizumab may have adverse effects on a fetus in utero. Refer to Appendix 2 for approved methods of contraception.

For this study, male participants will be considered to be of non-reproductive potential if they have azoospermia (whether due to having had vasectomy or due to an underlying medical condition).

### **5.1.4 Pregnancy**

If a participant inadvertently becomes pregnant while on treatment with pembrolizumab, the participant will be immediately discontinued from study treatment. The site will contact the participant at least monthly and document the participant's status until the pregnancy has been completed or terminated. The outcome of the pregnancy will be reported to Merck within 2 working days if the outcome is a serious adverse experience (e.g., death, abortion, congenital anomaly, or other disabling or life-threatening complication to the mother or newborn). The study Investigator will make every effort to obtain permission to follow the outcome of the pregnancy and report the condition of the fetus or newborn to Merck. If a male participant impregnates his female partner, the study personnel at the site must be informed immediately and the pregnancy must be reported to Merck and followed as described in Section 7.2.2.

### **5.1.5 Use in Nursing Women**

It is unknown whether pembrolizumab is excreted in human milk. Since many drugs are excreted in human milk, and because of the potential for serious adverse reactions in the nursing infant, participants who are breast-feeding are not eligible for enrollment.

## 5.2 Enrollment

Enrollment will be defined as the date participant starts treatment. Prior to this, while patient is being considered for the trial will be the screening period.

## 5.3 Trial Treatments

The treatment to be used in this trial is outlined below in **Table 2**

**Table 2. Trial Treatment**

Drug	Dose/Potency	Dose Frequency	Route of Administration	Regimen/Treatment Period	Use
Pembrolizumab	200 mg	Q3W	IV infusion	Day 1 of weeks 0, 3 and 6 of NAC***	Experimental
Methotrexate	30 mg/m 	Q2W	IV push	Day 1 of weeks 0, 2, 4 and 6 in NAC. Administered first.	SOC
Vinblastine	3mg/m 	Q2W	IV infusion	Day 1 of weeks 0, 2, 4 and 6 in NAC. Administered second.	SOC
Doxorubicin	30mg/m 	Q2W	IV push	Day 1 of weeks 0, 2, 4 and 6 in NAC. Administered third.	SOC
Cisplatin	70mg/m  *	Q2W	IV infusion	Day 1 of weeks 0, 2, 4 and 6 in NAC. Administered last.	SOC
Pegfilgrastim or Filgrastim**	Standard dose per manufacturer	Q2W	Subcutaneous injection	Day 1 or 2 of weeks 0, 2, 4 and 6 in NAC. Administered after chemotherapy	SOC

Trial treatment should begin on the day of enrollment.

\*Cisplatin dose may be split as 35 mg/m^2 on days 1 and 2 (day 3 or day 4 is allowed for the second split dose), based on investigator's discretion

\*\* Granulocyte colony-stimulating factor (G-CSF): Either On-Pro or any biosimilar to (a) Pegfilgrastim or to (b) On-Pro or to (c) Filgrastim is allowed (G-CSF is given as a standard best supportive care to aMVAC chemotherapy)

\*\*\*On days when pembrolizumab and aMVAC will be administered (week 0 and 6), pembrolizumab will be administered first (before aMVAC)

### 5.3.1 Timing of Dose Administration

Trial treatment should be administered on Day 1 of each cycle after all procedures/assessments have been completed as detailed on the Trial Flow Chart (Section 6.0). Trial treatment may be

administered up to 4 days before or after the scheduled Day 1 of each cycle due to administrative and logistical reasons.

Pembrolizumab 200 mg will be administered as 30-minute IV infusion every 3 weeks. Sites should make every effort to target infusion timing to be as close to 30 minutes as possible. However, given the variability of infusion pumps from site to site, a window of +/-10 minutes is permitted (i.e., infusion time is 30 minutes: -10 min/+10 min).

The Investigator's Brochure contains specific instructions for the preparation of the pembrolizumab infusion fluid and administration of infusion solution.

Accelerated (a)MVAC will be administered as sequential chemotherapy every 2 weeks. Medications will be administered per pharmacy protocol. G-CSF should ideally be given subcutaneously on day 1 or 2 in the form of either pegfilgrastim or filgrastim (or On-Pro or biosimilar) after the completion of the chemotherapy infusion.

On dates when aMVAC will be co-administered with pembrolizumab (week 0 and 6), aMVAC should be given after pembrolizumab.

### **5.3.2 Dose modification and toxicity management for immune-related AEs associated with pembrolizumab**

AEs associated with pembrolizumab exposure , including coadministration with additional compounds, may represent an immune-related response. These irAEs may occur shortly after the first dose or several months after the last dose of pembrolizumab/combination treatment and may affect more than one body system simultaneously. Therefore, early recognition and initiation of treatment is critical to reduce complications. Based on existing clinical study data, most irAEs were reversible and could be managed with interruptions of pembrolizumab/combination treatment, administration of corticosteroids and/or other supportive care. For suspected irAEs, ensure adequate evaluation to confirm etiology or exclude other causes. Additional procedures or tests such as bronchoscopy, endoscopy, skin biopsy may be included as part of the evaluation. Dose modification and toxicity management guidelines for irAEs associated with pembrolizumab/combination treatment are provided in Table 3.

**Table 3. Dose Modification and Toxicity Management Guidelines for Immune-related AEs Associated with Pembrolizumab monotherapy and IO Combinations**

General instructions:				
irAEs	Toxicity grade (CTCAE V5.0)	Action with pembrolizumab	Corticosteroid and/or other therapies	Monitoring and follow-up
Pneumonitis	Grade 2	Withhold	Administer corticosteroids (initial dose of 1 - 2 mg/kg prednisone or equivalent) followed by taper  Add prophylactic antibiotics for opportunistic infections	Monitor participants for signs and symptoms of pneumonitis  Evaluate participants with suspected pneumonitis with radiographic imaging and initiate corticosteroid treatment
	Recurrent Grade 2, Grade 3 or 4	Permanently discontinue		
Diarrhea / Colitis	Grade 2 or 3	Withhold	Administer corticosteroids (initial dose of 1 - 2 mg/kg prednisone or equivalent) followed by taper	Monitor participants for signs and symptoms of enterocolitis (ie, diarrhea, abdominal pain, blood or mucus in stool with or without fever) and of bowel perforation (ie, peritoneal signs and ileus)  Participants with $\ge$ Grade 2 diarrhea suspecting colitis should consider GI consultation and performing endoscopy to rule out colitis  Participants with diarrhea/colitis should be advised to drink liberal quantities of clear fluids. If sufficient oral fluid intake is not feasible, fluid and electrolytes should be substituted via IV infusion
	Recurrent Grade 3 or Grade 4	Permanently discontinue		

**Neoadjuvant aMVAC+Pembrolizumab – non-UC MIBC Protocol**

Consortium Study No.: RG1006206

Version 8: 20-DEC-2023

 Fred Hutch IRB  
 Approved  
 3/13/2024

AST or ALT elevation or Increased Bilirubin	Grade 2 a	Withhold	Administer corticosteroids (initial dose of 0.5 - 1 mg/kg prednisone or equivalent) followed by taper	Monitor with liver function tests (consider weekly or more frequently until liver enzyme value returned to baseline or is stable)
	Grade 3 b or 4 c	Permanently discontinue	Administer corticosteroids (initial dose of 1 - 2 mg/kg prednisone or equivalent) followed by taper	
Type 1 diabetes mellitus (T1DM) or Hyperglycemia	New onset T1DM or Grade 3 or 4 hyperglycemia associated with evidence of $\beta$ -cell failure	Withhold d	Initiate insulin replacement therapy for participants with T1DM  Administer anti-hyperglycemic in participants with hyperglycemia	Monitor participants for hyperglycemia or other signs and symptoms of diabetes
Hypophysitis	Grade 2	Withhold	Administer corticosteroids and initiate hormonal replacements as clinically indicated	Monitor for signs and symptoms of hypophysitis (including hypopituitarism and adrenal insufficiency)
	Grade 3 or 4	Withhold or permanently discontinue d		
Hyperthyroidism	Grade 2	Continue	Treat with nonselective beta-blockers (eg, propranolol) or thionamides as appropriate	Monitor for signs and symptoms of thyroid disorders
	Grade 3 or 4	Withhold or permanently discontinue d		
Hypothyroidism	Grade 2, 3, 4	Continue	Initiate thyroid replacement hormones (eg, levothyroxine or liothyronine) per standard of care	Monitor for signs and symptoms of thyroid disorders
Nephritis: grading according to increased creatinine or acute kidney injury	Grade 2	Withhold	Administer corticosteroids (prednisone 1 to 2 mg/kg or equivalent) followed by taper	Monitor changes of renal function
	Grade 3 or 4	Permanently discontinue		
Neurological Toxicities	Grade 2	Withhold	Based on severity of AE administer corticosteroids	Ensure adequate evaluation to confirm etiology and/or exclude other causes
	Grade 3 or 4	Permanently discontinue		

Myocarditis	Grade 1 or 2	Withhold	Based on severity of AE administer corticosteroids	Ensure adequate evaluation to confirm etiology and/or exclude other causes
	Grade 3 or 4	Permanently discontinue		
Exfoliative Dermatologic Conditions	Suspected SJS, TEN, or DRESS	Withhold	Based on severity of AE administer corticosteroids	Ensure adequate evaluation to confirm etiology or exclude other causes
	Confirmed SJS, TEN, or DRESS	Permanently discontinue		
All Other immune-related AEs	Persistent Grade 2	Withhold	Based on severity of AE administer corticosteroids	Ensure adequate evaluation to confirm etiology or exclude other causes
	Grade 3	Withhold or discontinue based on the event c		
	Recurrent Grade 3 or Grade 4	Permanently discontinue		

AE(s)=adverse event(s); ALT= alanine aminotransferase; AST=aspartate aminotransferase; CTCAE=Common Terminology Criteria for Adverse Events; DRESS=Drug Rash with Eosinophilia and Systemic Symptom; GI=gastrointestinal; IO=immuno-oncology; ir=immune related; IV=intravenous; SJS=Stevens-Johnson Syndrome; T1DM=type 1 diabetes mellitus; TEN=Toxic Epidermal Necrolysis; ULN=upper limit of normal.

**Note: Non-irAE will be managed as appropriate, following clinical practice recommendations.**

a AST/ALT: >3.0 to 5.0 x ULN if baseline normal; >3.0 to 5.0 x baseline, if baseline abnormal; bilirubin:>1.5 to 3.0 x ULN if baseline normal; >1.5 to 3.0 x baseline if baseline abnormal

b AST/ALT: >5.0 to 20.0 x ULN, if baseline normal; >5.0 to 20.0 x baseline, if baseline abnormal; bilirubin:>3.0 to 10.0 x ULN if baseline normal; >3.0 to 10.0 x baseline if baseline abnormal

c AST/ALT: >20.0 x ULN, if baseline normal; >20.0 x baseline, if baseline abnormal; bilirubin: >10.0 x ULN if baseline normal; >10.0 x baseline if baseline abnormal

d The decision to withhold or permanently discontinue pembrolizumab is at the discretion of the Investigator or treating physician. If control achieved or  $\leq$  Grade 2, pembrolizumab may be resumed.

e Events that require discontinuation include but are not limited to: encephalitis and other clinically important irAEs (eg, vasculitis and sclerosing cholangitis).

## Dose Modification and Toxicity Management of Infusion Reactions Related to Pembrolizumab

Pembrolizumab may cause severe or life-threatening infusion-reactions including severe hypersensitivity or anaphylaxis. Signs and symptoms usually develop during or shortly after drug infusion and generally resolve completely within 24 hours of completion of infusion. Dose modification and toxicity management guidelines on pembrolizumab associated infusion reaction are provided in Table 4.

**Table 4. Pembrolizumab Infusion Reaction Dose Modification and Treatment Guidelines**

NCI CTCAE Grade	Treatment	Premedication at Subsequent Dosing
Grade 1 Mild reaction; infusion interruption not indicated; intervention not indicated	Increase monitoring of vital signs as medically indicated until the participant is deemed medically stable in the opinion of the investigator	None
Grade 2 Requires therapy or infusion interruption but responds promptly to symptomatic treatment (eg, antihistamines, NSAIDs, narcotics, IV fluids); prophylactic medications indicated for $\leq 24$ hrs	Stop Infusion Additional appropriate medical therapy may include but is not limited to: IV fluids Antihistamines NSAIDs Acetaminophen Narcotics  Increase monitoring of vital signs as medically indicated until the participant is deemed medically stable in the opinion of the investigator.  If symptoms resolve within 1 hour of stopping drug infusion, the infusion may be restarted at 50% of the original infusion rate (eg, from 100 mL/hr to 50 mL/hr). Otherwise dosing will be held until symptoms resolve and the participant should be premedicated for the next scheduled dose.  Participants who develop Grade 2 toxicity despite adequate premedication should be permanently discontinued from further study drug intervention.	Participant may be premedicated 1.5 h ( $\pm 30$ minutes) prior to infusion of pembrolizumab with: Diphenhydramine 50 mg PO (or equivalent dose of antihistamine). Acetaminophen 500-1000 mg PO (or equivalent dose of analgesic).

NCI CTCAE Grade	Treatment	Premedication at Subsequent Dosing
Grades 3 or 4 Grade 3: Prolonged (ie, not rapidly responsive to symptomatic medication and/or brief interruption of infusion); recurrence of symptoms following initial improvement; hospitalization indicated for other clinical sequelae (eg, renal impairment, pulmonary infiltrates) Grade 4: Life-threatening; pressor or ventilatory support indicated	Stop Infusion. Additional appropriate medical therapy may include but is not limited to: Epinephrine** IV fluids Antihistamines NSAIDs Acetaminophen Narcotics Oxygen Pressors Corticosteroids Increase monitoring of vital signs as medically indicated until the participant is deemed medically stable in the opinion of the investigator. Hospitalization may be indicated. **In cases of anaphylaxis, epinephrine should be used immediately. Participant is permanently discontinued from further study drug intervention.	No subsequent dosing

Appropriate resuscitation equipment should be available at the bedside and a physician readily available during the period of drug administration.
 
For further information, please refer to the Common Terminology Criteria for Adverse Events v5.0 (CTCAE) at http://ctep.cancer.gov
		

### Other Allowed Dose Interruption for Pembrolizumab

Pembrolizumab may be interrupted for situations other than treatment-related AEs, such as medical / surgical events or logistical reasons not related to study therapy. Participants should be placed back on study therapy within 3 weeks of the scheduled interruption. The reason for interruption should be documented in the participant's study record.

#### 5.3.3 Dose Modifications for aMVAC chemotherapy (recommendations only; actual decisions for chemotherapy will be based on the best clinical judgment and institutional guidelines, if applicable)

##### 5.3.3.1 Hematological Toxicity

Grade 1 and Grade 2 toxicities will be accepted without dose interruption or dose modification. However, for grade 2 neutropenia on day 1 of any chemotherapy cycle (absolute neutrophil count  $1-1.5 \times 10^9/L$ ), dose reduction to 75% dose of methotrexate, vinblastine and doxorubicin is recommended.

If a patient experiences Grade 3 hematological toxicity on day 1 of any chemotherapy cycle, study chemotherapy will be held until toxicity has resolved or  $\leq$  Grade 1. For grade 3 neutropenia on day 1 of any chemotherapy cycle (absolute neutrophil count

1-1.5x10^9/L) that resolves to  $\leq$  Grade 1 within 4 weeks, dose reduction to 66% dose of methotrexate, vinblastine and doxorubicin is recommended. If the Grade 3 toxicity does not resolve to  $\leq$  Grade 1 within 4 weeks, all study chemotherapy may be **permanently discontinued**. Pembrolizumab may continue in that case as per physician discretion based on attribution.

If the patient experiences Grade 4 treatment related hematologic toxicity, all study chemotherapy may be **permanently discontinued** regardless of the time to resolution  $\leq$  Grade 1. Pembrolizumab may continue in that case as per physician discretion based on attribution.

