### **7.2.7 Grading Adverse Event Severity**

All AEs will be graded in severity according to the NCI Common Terminology Criteria for Adverse Events (CTCAE) Version 5.0 (Table 6). If a CTCAE criterion does not exist, the Investigator should use the grade or adjectives: Grade 1 (mild), Grade 2 (moderate), Grade 3 (severe), Grade 4 (life-threatening), or Grade 5 (fatal) to describe the maximum intensity of the adverse event.

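### Section 5.3.3.1 prints the same neutrophil range for grade 2 and grade 3 neutropenia, so one day-1 count points both to treating at 75% and to holding chemotherapy

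*Combined protocol and SAP*

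**What the plan says.** **Neutropenia (Section 5.3.3.1).** The grade 2 rule opens "for grade 2 neutropenia on day 1 of any chemotherapy cycle (absolute neutrophil count", gives 1-1.5 x10^9/L, and ends "dose reduction to 75% dose of methotrexate, vinblastine and doxorubicin is recommended". No hold is attached to it.

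The next paragraph sets the grade 3 hold by grade alone: "If a patient experiences Grade 3 hematological toxicity on day 1 of any chemotherapy cycle, study chemotherapy will be held" until recovery to grade 1 or lower. It then gives the restart dose. The sentence opens "For grade 3 neutropenia on day 1 of any chemotherapy cycle (absolute neutrophil count", its bracket continues "1-1.5x10 9 /L) that resolves to" grade 1 or lower within 4 weeks, and it ends "dose reduction to 66% dose of methotrexate, vinblastine and doxorubicin is recommended". The grade 4 rule carries no ANC figure.

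**Status and grading.** The heading of Section 5.3.3 describes its content as "recommendations only; actual decisions for chemotherapy will be based on the best clinical judgment and institutional guidelines, if applicable". Section 7.2.7 grades adverse events by CTCAE v5.0. Where CTCAE has no criterion, it falls back on the ordered scale "Grade 1 (mild), Grade 2 (moderate), Grade 3 (severe), Grade 4 (life-threatening), or Grade 5 (fatal"). Table 6 lists the CTCAE v5.0 grades in the same rising order.

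**Entry limits (Table 1, bound in by inclusion criterion 12).** ANC must be at least 1500/µL. Renal function is adequate if serum creatinine is at most 1.5 x ULN, or if creatinine clearance (CrCl) or GFR is at least 50 mL/min. The asterisk note under the dosing table in Section 5.3.3.2 describes CrCl below 50 mL/min as an exclusion criterion.

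**The concern.** A bracketed ANC range lets a clinician go from a laboratory value to an action without looking up the grade. Two grades with different actions cannot share one range. Someone working from the printed number, say 1.2 x10^9/L on day 1 of a cycle, finds support for giving a reduced dose that day and also for giving no chemotherapy that day.

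For the lower counts, where the more severe rules should apply, the section offers no number at all. What is at stake is consistent dosing of a cytotoxic regimen in a trial of 14 to 17 patients. Entry already requires at least 1500/µL, so the question arises mainly at the second to fourth of the four aMVAC doses.

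**Working it through.** **Step 1. Map counts to the printed ranges.** Both ranges come from Section 5.3.3.1.

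| Day-1 ANC (x10^9/L) | Falls in printed grade 2 range | Falls in printed grade 3 range |
|---|---|---|
| 0.4, 0.7, 0.99 | no | no |
| 1.0, 1.2, 1.5 | yes: treat, three drugs at 75% | yes: hold, then 66% on restart |
| 1.6 | no | no |

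Every count from 1.0 to 1.5 matches both rows. No count below 1.0 matches either.

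**Step 2. Decide which bracket is wrong.** Table 1 accepts 1500/µL = 1.5 x10^9/L, which is the top of the printed range.

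- Suppose 1-1.5 belonged to grade 3. Grade 2 is milder, so it would have to lie at 1.5 or above. The section would then recommend a 75% dose at counts that Table 1 treats as adequate for entry, which is not coherent.
- Suppose 1-1.5 belongs to grade 2. Grade 2 then begins just under the entry limit, and grade 3, being more severe, lies below 1.0. This fits Table 1, and it fits the absence of a hold for grade 2.

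The grade 3 bracket is therefore the one to change. The documents print no numeric CTCAE cut-offs for neutropenia. They show that the grade 3 range lies below 1.0, but the exact bounds, including the one that separates grade 4, have to come from CTCAE v5.0.

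**Step 3. Check the primary design.** Section 8.0 gives two exact binomial rules against a null pCR rate of 8%:

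- n = 17, at least 4 pCR: P(X ≥ 4 | 0.08) = 0.042 and P(X ≥ 4 | 0.36) = 0.911 (stated 4% and 91%).
- n = 14, at least 3 pCR: P(X ≥ 3 | 0.08) = 0.096 and P(X ≥ 3 | 0.40) = 0.960 (stated 10% and 96%).

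Both reproduce at the printed rounding, and neither uses anything from Section 5.3.3.1.

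**Step 4. Secondary point, renal wording.** Take a patient with creatinine at or below 1.5 x ULN and CrCl of 44, 47 or 49 mL/min. Table 1 admits the patient through its OR; the note in Section 5.3.3.2 excludes the patient. If creatinine is above 1.5 x ULN, or CrCl is 50 or more, the two texts agree. The exclusion list in Section 5.1.2 has no CrCl item for the note to refer to.

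**The case against.** The best defence is that grade governs, not the bracket. The hold sentence contains no ANC, the dose sentences open with the grade, and grading is by CTCAE v5.0. A clinician who grades first will reach the right row. The section is advisory, G-CSF accompanies each aMVAC dose (Table 2), the text under Table 5 requires laboratory results to be reviewed and found acceptable before every dose, and there is one site. All of this stands, and it limits the consequence. It does not make the printed number right.

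Some stronger readings are tempting, and the documents do not support them.

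- *Two competing doses, 12% apart.* A reader might compare 75% with 66% and compute (75 − 66)/75 = 12%. The two are not alternatives for one patient on one day: 66% applies only on restart after a hold and recovery. The literal conflict is 75% now against no chemotherapy now.
- *No instruction below 1.0.* Grade 3 and grade 4 rules exist and are stated by grade. Only the printed count is missing.
- *Eligibility is unworkable, or patients unfit for cisplatin will be treated.* Table 1 is the rule that inclusion criterion 12 invokes, and its closing note lets laboratory limits be adapted to guidelines for specific chemotherapies. Inclusion criterion 4 and exclusion criterion 3 require fitness for cisplatin and aMVAC. The dosing table recommends a hold below 45 mL/min, and split cisplatin with 75% methotrexate at 45-59. The note is a wording mismatch.

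**Conclusion.** The error is real and should be corrected, but it is small. The grade 3 bracket repeats the grade 2 range, so every day-1 count from 1.0 to 1.5 x10^9/L maps to two different actions and lower counts map to no printed range. That the grade 3 bracket is the faulty one rests on two things in the document: grades rise with severity, and Table 1 accepts 1.5 x10^9/L.

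The documents give no basis for estimating how many doses would be affected, and patient harm should not be inferred. The sample size, error rates, power and pCR decision rule are unaffected.

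The renal mismatch is a minor secondary point, confined to patients with creatinine at or below 1.5 x ULN and CrCl below 50 mL/min.

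**What to change.** **Section 5.3.3.1.** Keep 1-1.5 x10^9/L for grade 2 only. Replace the grade 3 bracket with the CTCAE v5.0 grade 3 range, below 1.0 x10^9/L, with both bounds confirmed by the investigators. This changes one bracket at the next amendment and costs no patients or procedures.

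**Section 5.3.3.2 and Table 1.** Make them agree. Either reword the note to match Table 1 and rely on the dosing table, which costs no accrual, or require CrCl or GFR of at least 50 mL/min in Table 1. The second option may lose patients. At the planned rate of one patient every 30-45 days, each one lost adds about 30-45 days, and the documents do not show how many that would be. The choice is a clinical one for the investigators.
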